#### **6.4.3 Procedures for Participants with Suspected or Confirmed HIV Infection**

HIV testing will be performed at all scheduled study visits (with the exception of the GAHT Initiation Visit). In addition, if a participant has signs or symptoms consistent with acute HIV infection or expresses a concern about recent HIV acquisition, HIV testing will be performed using a ribonucleic acid (RNA) test that, is able to detect early HIV infection. If possible, an assay that is U.S. FDA-cleared for early HIV diagnosis such as the Aptima HIV-1 RNA Qualitative Assay should be used.

Regardless of whether HIV RNA testing is used for diagnostic testing, HIV acquisition after study enrollment must be confirmed in all cases using two independent samples collected on different days, as per HIV testing algorithm found in the SSP Manual.

Participants who have any reactive or positive HIV test result during follow-up visits will have further testing to confirm infection, as described in the SSP Manual and Appendix Ib. Samples from participants who are confirmed to be HIV-infected should be sent to a local laboratory for resistance testing to assist with clinical management (results from resistance testing performed in local laboratories should not be reported to the HPTN Statistical Data Management Center [SDMC] or the HPTN Laboratory Center [LC]). The site IoR or designee should consult the HPTN LC if confirmatory testing does not confirm that the participant is HIV-infected.

As outlined in Appendix Ib, participants who are confirmed to be HIV-infected will be linked for local HIV care and will have an additional visit to follow-up on linkage to care three months after the HIV confirmation visit. At this visit, participants will be terminated from the study. Additionally, participants will be offered linkage to GAHT services.

#### **6.5 Visit Windows**

For each required study visit, there is an allowable visit window specifying on which study days (post-enrollment) the visit is "allowed" to be completed. The allowable visit windows are

contiguous from visit to visit, and do not overlap. Within each allowable visit window, there is a target visit window and study visits should ideally be conducted within this window. These windows are outlined in Table 6 below. If more than one visit is necessary to complete all visit procedures, these could be completed during multiple days within the allowable visit window.

**Table 6: Study Visit Windows**

Visit	Target Visit Day	Target Visit Window	Allowable Visit Window
Screening			Up to 30 days before enrollment
Enrollment	Day 0		
GAHT Initiation Visit			Up to 10 days post blood collection for estradiol and total testosterone testing
Week 13	Day 91	Day 77 - 105	Day 77 - 153
Week 26	Day 182	Day 168 - 196	Day 154 - 244
Week 39	Day 273	Day 259 - 287	Day 245 - 336
Week 52	Day 365	Day 351 - 379	Day 337 – 427
Week 65	Day 456	Day 442 - 470	Day 428 - 518
Week 78	Day 547	Day 533 - 561	Day 519 – study closure

## 6.6 Qualitative Data Collection

In-depth interviews (IDIs) will be conducted with a subset of approximately 60 participants, randomized to either of the study arms, across all five sites or until saturation of information is reached. Additional participants may be enrolled based on characteristics of PrEP use. Individual sites may enroll approximately 12 participants in this sub-study. Approximately half of participants will be of the Immediate Intervention Arm and approximately half will be of the Deferred Intervention Arm. Protocol chairs will work closely with sites to evaluate enrollment targets and overall qualitative goals. The IDIs are designed to better understand decision making around PrEP, experiences with PrEP use, experiences with co-located services, and acceptability of co-located services.

In-depth interviews will be conducted among four groups of participants:

1. TGW who accept/initiate PrEP at enrollment.
2. TGW who decline PrEP at enrollment.
3. TGW who discontinue PrEP at any point after enrollment.
4. TGW who decline PrEP at enrollment and accept PrEP at any point after enrollment.

Approximately 30% of those enrolled in the IDI sub-study at each site should be TGW who decline PrEP at enrollment or discontinue PrEP at any time after enrollment.

Participants who accept/initiate or decline PrEP at enrollment who are selected and consent to participate in the qualitative component at enrollment, will have one interview at baseline (Enrollment), one interview at Week 52 (12 months) and one interview at the end of the study, Week 78 (18 months) for a total of three visits.

To gain a better understanding of participants who discontinue PrEP during the study, some participants at each site will be selected after enrollment to participate in the qualitative component. Participants who are selected and consent to participate in the **qualitative component** at the point of discontinuation of PrEP during the study will have one interview at the visit they discontinue PrEP and at least one at the end of the study Week 78 (18 months). If time allows an interview should be completed at least 6 months from the initial interview and 6 months from the end of the study.

Among TGW participants who accept/initiate PrEP at enrollment or discontinue PrEP during the study, the qualitative component will explore:

- Decisions and rationale to accept/initiate and/or discontinue PrEP
- Barriers and facilitators to PrEP adherence
- Experiences with co-located services of GAHT and HIV prevention services, including acceptability and PrEP adherence (for those in the Deferred Intervention Arm: Experiences accessing GAHT separately from PrEP services)
- Perception of risk for acquiring HIV

Among TGW participants who decline PrEP at enrollment the qualitative component will explore:

- Decisions and rationale to decline PrEP
- Knowledge and perceptions of PrEP
- Concerns about the use of PrEP
- Perceptions of the benefits of PrEP use
- Acceptability of PrEP use in their community
- Perception of risk for acquiring HIV
- Experience with co-located services of GAHT and HIV prevention services

[figure not shown]
The semi-structured qualitative interview guide will provide a general structure for the discussion. The interview guide will have a summary section with pre-coded answers and summary fields. The interviewer will document findings during or immediately after the interview to begin processing the information, begin to look for emerging themes, and to recognize when the study is reaching saturation.

All IDIs will be conducted in a private setting within the participants' research site. Interviews will last approximately 60-90 minutes. Interviews will be conducted in a study preferred language, digitally recorded, then transcribed and subsequently translated into English as needed.

Additional information will be included in the SSP.

## 6.7 Drug-Hormone Interaction Sub-study

In the iPrEx trial and the subsequent open-label extension cohort study, 14% of participants who received PrEP self-identified as TGW. While incidence of HIV seroconversion did not differ between cisgender MSM and TGW, TGW exhibited lower PrEP metabolite concentrations. In PrEP clinical trials, while non-adherence is likely the dominant cause of suboptimal drug concentrations, numerous other factors could modify drug concentrations in addition to adherence, including the potential impact of elevated estrogen concentrations on PrEP pharmacology in TGW. Subsequent, smaller studies were conducted to evaluate the potential relationship on estrogen-based GAHT on PrEP pharmacokinetics (PK). In the JHU-CFAR TGW study, plasma TFV and FTC trough concentrations ( $C_{\text{tau}}$ ) were 32% ( $p = 0.01$ ) and 32% ( $p = 0.04$ ) lower, respectively, in TGW as compared to cisgender men (CGM) after directly observed FTC/TDF dosing to steady-state; median plasma TFV concentrations diverged in CGM vs. TGW approximately 5 hours after-dosing (Figure 3). There was no impact of PrEP on hormone levels. The Thai Red Cross reported that estradiol valerate 2 mg and cyproterone acetate 25 mg reduced TFV concentrations by 18% ( $C_{\text{tau}}$ ), while FTC/TDF did not affect plasma estrogen or testosterone concentrations. AUC changes were of similar magnitude in both studies.

**Figure 3.** Concentration vs. time plots for plasma tenofovir (TFV, Panel A) and emtricitabine (FTC, Panel B), and peripheral blood mononuclear cell (PBMC) TFV diphosphate (TFV-DP, Panel C) and FTC triphosphate (FTC-TP, Panel D) comparing transgender women (TGW; dashed lines, squares) and CGM (solid lines, circles). Data are medians with error bars indicating lower and upper quartiles. Time values are slightly offset to avoid overlap of data.

[figure not shown]
With the recent approval of FTC/TAF (Descovy®) as a prevention option for TGW, the goal of this substudy is to characterize the relationship between GAHT and PrEP concentrations. In order to investigate this relationship, directly observed therapy (DOT) of study product is required to ensure that potential pharmacologic differences are not due to lapses in PrEP adherence. DOT can take place either at the study site or by videoconferencing on a cell phone, computer, or tablet, using a platform like FaceTime, WhatsApp, and Google Duo. These platforms feature end-to-end encryption, meaning that only the communicating users can read the messages. No recordings of session will take place, so no data about the participant will be stored via these apps.

Consequently, the DHI substudy will include a one-week DOT **pre-GAHT** dosing phase to occur immediately after enrollment (Period 1), and a **post-GAHT** dosing phase, which will occur directly following the participant's first quarterly visit (week 13) and will include one-week of DOT of PrEP (Period 2). Refer to Figure 4 for an overview of the visit schedule for the DHI sub-

study. The mechanism used for DOT may be face-to-face or video-based; DOT options will be described in the SSP.

Post-GAHT PK assessment initiates at week 13 (month 3) in order to streamline the total number of visits required by the study participant. All participants will have a study visit at week 13, as described in the main study's schedule of events (Appendix 1a). Therefore, the directly observed therapy (DOT) phase for the post-GAHT PK assessment is coordinated with this visit in order to circumvent the need for an additional participant visit and blood collections, minimizing burden to study participants.

**Figure 4.** Drug-Hormone Interaction Substudy Visit Schedule

Pharmacologic assessments of TFV, when administered as TDF or TAF, can be conducted in plasma, PBMC, and red blood cells (RBC) collected as DBS. While each offers its advantages, and provides complementary information regarding PrEP usage, because of the DOT-component of the DHI sub-study, analysis will be focused on assessments of TAF and TFV in plasma and TFV-DP (intracellular metabolite of TAF and TDF) in PBMC. Due to the accumulation of TFV-DP in RBC over time, and the significantly longer half-life of TFV-DP in RBC as compared to PBMC and plasma, TFV-DP concentrations from DBS represent *average* concentrations in the months prior to sampling and are therefore relatively resistant to recent changes in adherence. Conversely, plasma PrEP concentrations (and to an extent PBMC PrEP metabolite measurements) are more reflective of recent adherence and are therefore more amenable to evaluate pharmacologic differences following a short period of DOT.

For those participants enrolled in the DHI sub-study, directly following one-week of DOT to ensure PrEP regimen compliance, participants will present for sparse PK sampling. Blood for plasma and PBMC isolation will concurrently occur pre-dose, as well as 1 hour and 4 hours after observed PrEP dosing. Sampling will include plasma isolation for FTC, TAF, and TFV testing, and PBMC isolation for TFV-DP and FTC-TP measurements. This sparse sampling scheme will be used to estimate steady-state pre-dose trough concentration ( $C_{\text{tau}}$ ) for the aforementioned analytes. We will estimate peak ( $C_{\text{max}}$ ), and four-hour area under the concentration time curve ( $AUC_{0-4}$ ) concentrations for analytes in plasma and PBMC before and after GAHT dosing (Period 1 and Period 2). While the  $C_{\text{max}}$  and  $AUC_{0-4}$  estimates will be crude given the very sparse sampling, their inclusion will increase the sensitivity of capturing differences in PrEP metabolism caused by the addition of GAHT. In addition, if initial inspection of the data allows and external raw PK data on FTC/TAF dosing are available, a more formal population pharmacokinetic model will be explored to evaluate changes in PK parameters resulting from DHI. Additional serum samples will be collected during the Period 1 (pre-GAHT) and Period 2 (post-GAHT) pre-dose

time points for measurement of endogenous hormones, including estradiol, total and free testosterone, luteinizing hormone, and follicle stimulating hormone. This testing will be conducted retrospectively to provide additional information on the potential influence of GAHT on PrEP (FTC/TAF) pharmacology.

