### **3.2 Sub-Studies**

HPTN 091 participants may also be selected to participate in up to two sub-studies or nested cohorts. A qualitative sub-study (n=60) will be embedded to gather in-depth interview data about PrEP experiences, including barriers and facilitators to PrEP uptake and adherence. Another subset of up to 50 participants randomized to the Immediate Intervention Arm who accept hormonal therapy and Descovy® for PrEP at U.S. sites will be enrolled in a Drug-Hormone Interaction (DHI) sub-study. The purpose of the DHI sub-study is to evaluate the relationship between PrEP agents and GAHT. This relationship will be evaluated through the measurement of plasma and peripheral blood mononuclear cell (PBMC) PrEP concentrations prior to and after administration of co-localized GAHT. Hormone concentrations will also be measured at designated time points. See Section 6.6, Section 6.7, and Appendix IC for additional information.

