## 6.0 STUDY PROCEDURES

An overview of the study visits and evaluations schedule is provided in Appendix Ia-Ic. Presented in this section is additional information on visit-specific study procedures. Detailed instructions to guide and standardize procedures across sites are provided in the HPTN 091 SSP Manual.

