## **10.0 LABORATORY SPECIMENS AND BIOHARZARD CONTAINMENT**

Laboratory procedures are listed in the SSP Manual and Appendices Ia and Ib.

There are no plans to perform host/human genetic testing in this study.

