## 10.2 Laboratory Center Specimens

The following types of specimens will be collected for testing at the HPTN Laboratory Center (LC)

- Plasma storage
- Serum storage (for the DHI Sub-study)
- DBS storage
- PBMC storage (for the DHI Sub-study)

Each study site will adhere to standards of Good Clinical Laboratory Practice (GCLP) reference, the HPTN Manual of Operations (MOP), the SSP Manual and local SOPs for proper collection, processing, labeling, transport, and storage of specimens to the local laboratory. Specimen collection, testing, and storage at the local laboratory will be documented using the HPTN Laboratory Data Management System (LDMS) as described in the SSP Manual.

All specimens will be shipped in accordance with International Air Transport Association (IATA) specimen shipping regulations. All shipments will be documented using the HPTN LDMS as described in the SSP Manual.

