## Appendix Ic: Schedule of Events for Participants in Drug-Hormone Interaction Substudy

Study Procedures	Day 1-7 Before GAHT Initiation Visit	GAHT Initiation Visit 	Week 13 Study Visit	Day 1-7 After Week 13	Day 8 After Week 13 (Clinic Visit)
Study Product/Supplies					
DOT	X			X	
In-clinic DOT		X	X		X
Laboratory					
Pre-DOT					
Plasma storage		X			X
Serum storage 		X			X
DBS storage		X	X		X
Post-DOT					
1 hour - Plasma storage for PK		X			X
1 hour - PBMC storage for PK		X			X
4 hours - Plasma storage for PK		X			X
4 hours – PBMC storage for PK		X			X

Only participants enrolled in the U.S. and using Descovy as the PrEP agent qualify for enrollment into the DHI sub- study.

Samples will be tested for estradiol, free and total testosterone, LH, and FSH. Results will not be returned to participants.

To be scheduled up to 10 days after collection of samples for estradiol and total testosterone samples for provision of GAHT as described in the protocol.

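### Appendix Ic omits the pre-dose PBMC sample that section 6.7 requires at both PK visits of the drug-hormone sub-study, so the PBMC trough would have no data if sites follow the schedule

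*Combined protocol and SAP*

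**What the plan says.** Section 6.7 describes two PK assessments, each after a week of directly observed dosing: Period 1 before study GAHT starts and Period 2 after the Week 13 visit. On sampling it says: "Blood for plasma and PBMC isolation will concurrently occur pre-dose, as well as 1 hour and 4 hours after observed PrEP dosing". Plasma is assayed for FTC, TAF and TFV, and PBMC for TFV-DP and FTC-TP. On use it says: "This sparse sampling scheme will be used to estimate steady-state pre-dose trough concentration", for all of these analytes. Cmax and AUC0-4 are also planned in both matrices and both periods. The section names its priorities: "analysis will be focused on assessments of TAF and TFV in plasma and TFV-DP (intracellular metabolite of TAF and TDF) in PBMC". Section 3.2 describes the sub-study in the same terms, as "measurement of plasma and peripheral blood mononuclear cell (PBMC) PrEP concentrations prior to and after administration of co-localized GAHT".

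Appendix Ic turns this into a schedule with two PK visits, the GAHT Initiation Visit and Day 8 after Week 13. Its Pre-DOT block has three rows: plasma, serum and DBS. PBMC occur only in the Post-DOT block, as "1 hour - PBMC storage for PK" and a matching 4-hour row.

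Section 6.0 directs the reader to the appendices: "An overview of the study visits and evaluations schedule is provided in Appendix Ia-Ic". Section 10.2 lists "PBMC storage (for the DHI Sub-study)" among the Laboratory Center specimens but gives no time points. Appendix Ia has no PBMC row.

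**The concern.** A pre-dose trough needs a pre-dose sample. Section 6.7 requires one in PBMC; the schedule that sites would use at the visit does not contain it. A site following Appendix Ic would store plasma, serum and DBS before the dose and begin PBMC isolation only at 1 hour.

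The affected matrix is one of the two on which section 6.7 focuses the analysis. Of the three parameters planned in PBMC, the trough is also the one without a caveat: the same section calls its Cmax and AUC0-4 estimates crude. The loss would be permanent. Period 1 is the pre-GAHT reference, and that sample cannot be obtained once hormones have started.

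**Working it through.** This is a comparison of two parts of the protocol plus a count. No power or sample-size figure is involved.

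**PBMC and plasma draws at each PK visit**

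| Time point | 6.7: plasma | 6.7: PBMC | Appendix Ic: plasma | Appendix Ic: PBMC |
|---|---|---|---|---|
| Pre-dose | yes | yes | yes | **no row** |
| 1 hour | yes | yes | yes | yes |
| 4 hours | yes | yes | yes | yes |

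**Inputs.** Three time points, two matrices and two periods (6.7); up to 50 participants (3.2 and 8.7.2).

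**Counts.**
- PBMC under 6.7: 3 time points × 2 periods = 6 per participant; 6 × 50 = 300 at most.
- PBMC under Appendix Ic: 2 × 2 = 4 per participant; 4 × 50 = 200 at most.
- Difference: 2 per participant; 300 − 200 = 100 at most, one third of the planned PBMC samples and all of the pre-dose ones.
- Plasma: 3 × 2 = 6 per participant in both places, so plasma agrees.

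**Consequences for the planned parameters.**
- Ctau: planned for 5 analytes (plasma FTC, TAF, TFV; PBMC TFV-DP, FTC-TP). Under Appendix Ic the 2 PBMC analytes have no pre-dose value in either period.
- AUC0-4: with draws at 0, 1 and 4 hours, the linear trapezoid is (C0 + C1)/2 × 1 + (C1 + C4)/2 × 3. Without C0 the first term cannot be computed, so only the 1-to-4-hour part rests on observed values for those 2 analytes.
- Cmax in PBMC would rest on two samples instead of three.
- The population PK model that 6.7 mentions is conditional on the data and on external data being available. It could model a PBMC trough from the 1-hour and 4-hour values but not observe one.

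**Can another sample replace it?** Pre-dose DBS is scheduled and contains TFV-DP from red cells. By the reasoning in 6.7, DBS reflects an average over preceding months and PBMC a shorter period, which is why 6.7 chose plasma and PBMC for an assessment after one week of observed dosing. DBS is therefore not a substitute.

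**Not affected.** All plasma parameters, the paired pre/post comparisons of PBMC at 1 and 4 hours, and Table 8, which concerns plasma TFV.

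**A smaller wording conflict in the same sub-study.** Section 8.7.2 draws participants from either arm; section 3.2 restricts them to the Immediate Intervention Arm. Section 8.7.2 also requires GAHT to start at the Enrollment Visit. On the target days of Table 6, the Period 2 PK visit is Day 91 + 8 = 99. Study-provided GAHT in the Deferred arm follows the Week 26 visit, Day 182, which is 182 − 99 = 83 days later. Only the Immediate arm fits, so the wording in 8.7.2 appears to be a slip.

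**The case against.** The strongest reply is that data loss is not established. Section 6.7 states the draw in plain terms, and a site following it would take the sample. Section 6.0 calls the appendices an overview and leaves detailed instructions to the SSP Manual. Section 10.0 says: "Laboratory procedures are listed in the SSP Manual and Appendices Ia and Ib", which does not name Appendix Ic at all. The SSP Manual and Figure 4 could not be read and may show the pre-dose PBMC draw. This stands as a limit: the contradiction is certain, the loss is conditional. It does not remove the contradiction, because section 3.2 refers to Appendix Ic for this sub-study and section 6.0 includes it in the schedule.

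A second reply is that the endpoint in 8.7.2 asks for PBMC concentrations before and after hormonal therapy and names no trough, so the 1-hour and 4-hour pairs still serve it. That is correct, and the sub-study's general purpose would survive. What would be lost is a parameter that 6.7 says will be estimated.

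Third, the objective is exploratory and involves up to 50 of about 310 participants, with no primary or secondary endpoint touched. That keeps the point modest in scope but does not make the sample recoverable.

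A row lost in converting the PDF cannot be excluded entirely. The table reads as complete, however, with three intact Pre-DOT rows and plasma and PBMC paired at each later time.

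**Conclusion.** The concern holds. Section 6.7 and Appendix Ic cannot both be followed, and nothing else in the readable protocol schedules a pre-dose PBMC sample. If Appendix Ic is followed literally, and the SSP Manual does not correct it, the shortfall is 2 of 6 PBMC samples per participant, up to 100 in all. TFV-DP and FTC-TP in PBMC would then have no observed trough in either period and no time-zero value for AUC0-4. The count assumes the maximum of 50 participants with both PK visits completed; fewer participants reduce it in proportion. The matter is confined to an exploratory objective and leaves the main trial and the plasma results intact. It should still be corrected before sampling, because the draw cannot be made later and the correction is small.

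**What to change.** Add a PBMC storage row for PK to the Pre-DOT block of Appendix Ic, marked at the GAHT Initiation Visit and at Day 8 after Week 13, and confirm that the SSP Manual and Figure 4 match section 6.7. In 8.7.2, replace the reference to either study arm with the Immediate Intervention Arm, as in 3.2. Table 8 needs no change.

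The cost is one schedule row and one phrase. The added work is PBMC processing, and the blood needed for it, at up to 100 pre-dose draws that already take place for plasma, serum and DBS and that 6.7 already requires for PBMC. No visit or participant is added. The blood volume given in the consent forms should be checked against the corrected schedule, since those pages were not available here.

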### 8.7.2 Drug-Hormone Interaction Sub-study

Driven by logistical and operational constraints, the sub-study will include up to 50 participants in the U.S. randomized to either of the study arms. This participant subset will be sequentially selected from participants who consented to the DHI sub-study and choose Descovy® as the PrEP agent and choose to initiate PrEP and GAHT at the Enrollment Visit. Table 8 shows the resulting statistical power for a range of assumed effect sizes and standard deviations in plasma TFV (when FTC/TDF was the PrEP regimen used).

**Table 8. Power to detect differences of ‘delta’ in TFV concentrations before and after initiating GAHT for different assumed pooled standard deviations, accounting for 15% missingness.**

		Pooled Std Deviation				
		40	50	60	70	80
n=50	20	89	72	56	44	36
	30	100	97	89	78	67
	40	100	100	99	95	89
	50	100	100	100	100	98

Descriptive statistics and graphics will be used to summarize the distribution of laboratory assays measured of the sub-sample of TGW participating in the DHI sub-study at each timepoint and over time. Paired comparisons (descriptive and regression based) will be performed to compare changes in these assays pre- and post-initiation of GAHT. Descriptive statistics will be used to explore potential changes in the concentration of PrEP drugs in those receiving GAHT among this subset of TGW. Mathematical models constructed from the data and leveraging data from previous research (e.g., Thai Red Cross and JHU CFAR, DISCOVER) can be used to evaluate the impacts of hormonal therapy on drug concentrations in this broader population.

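### The pre/post-GAHT comparison of PBMC drug metabolites assumes steady state after 7 to 10 days of new PrEP; if that is not reached, accumulation can offset a hormone-related fall

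*Combined protocol and SAP*

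**What the plan says.** Section 8.7.2 restricts the sub-study to U.S. participants on Descovy who "choose to initiate PrEP and GAHT at the Enrollment Visit". Section 6.7 places the first week of directly observed dosing (DOT) as a "dosing phase to occur immediately after enrollment (Period 1"), and Appendix Ic puts the Period 1 samples at the GAHT Initiation Visit, which is "To be scheduled up to 10 days after collection of samples for estradiol and total testosterone samples". Period 2 follows the "first quarterly visit (week 13) and will include one-week of DOT of PrEP (Period 2"), with samples on Day 8 after that visit.

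Sampling covers plasma and "PBMC isolation for TFV-DP and FTC-TP measurements". For all of these analytes Section 6.7 states: "This sparse sampling scheme will be used to estimate steady-state pre-dose trough concentration". On choice of matrix, the same section contrasts red cells, where it recognises accumulation, with plasma and PBMC: "plasma PrEP concentrations (and to an extent PBMC PrEP metabolite measurements) are more reflective of recent adherence".

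The analysis in Section 8.7.2 is: "Paired comparisons (descriptive and regression based) will be performed to compare changes in these assays pre- and post-initiation of GAHT". Section 6.7 also mentions a population PK model, but only if the data look suitable and outside FTC/TAF data can be had.

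**The concern.** Everyone is sampled in the same order, and everyone starts GAHT between the two samples. Time on PrEP therefore changes together with GAHT, and there is no concurrent group without GAHT to show what time alone does. This is harmless if each analyte has reached plateau by Period 1. If a PBMC metabolite has not, its Period 1 value is too low and the paired change adds an upward accumulation term to any hormone effect.

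A second problem follows from the same condition. If PBMC levels carry over for more than a week, one week of DOT does not erase the preceding weeks, so Period 2 also depends on adherence between the periods, which is not observed. DOT was included to remove that influence.

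At stake is the intracellular part of the answer. Section 1.1 cites concern about drug-hormone interaction as a barrier to PrEP uptake, and an apparent absence of change in PBMC could be read as reassurance that the data do not support.

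**Working it through.** **The plan's own figure.** Table 8 in Section 8.7.2 gives power for the pre/post difference with n = 50 and 15% missingness. A two-sided paired t-test at alpha 0.05 (assumed, as in the main study) with 50 x 0.85 = 42.5 pairs, reading the SD as that of the paired difference, reproduces all 20 cells to within 0.5 points. The table is internally sound. It concerns plasma TFV under FTC/TDF and allows for no time trend, so it gives no assurance about PBMC TFV-DP under FTC/TAF.

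**Inputs from the documents**
- Doses before Period 1: one week of DOT gives about 7. PrEP is supplied at Enrollment (Appendix Ia) and the GAHT Initiation Visit may fall up to 10 days after the hormone draw, so up to about 10.
- Period 2: nominally Day 91 + 8 = Day 99. The allowable Week 13 window in Table 6 (Day 77 to 153) makes the range Day 85 to 161.
- Dosing between periods: not directly observed.
- PrEP before entry: not excluded by Section 4.2.

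**Assumed inputs**
- PBMC half-life t: not in the documents beyond being shorter than in red cells. Range used: 1 to 6 days.
- True GAHT effect: a 20% fall. Section 6.7 cites plasma TFV trough falls of 18% and 32% under FTC/TDF; they serve here only as a guide to size.

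**Formulas** (first-order accumulation, no drug on board at entry)
- Fraction of plateau after N daily doses: f(N) = 1 - 2^(-N/t).
- Period 2 fraction, with a = share of doses taken between periods: f(7) + a x 2^(-7/t). At a = 1 this equals 1.
- Apparent ratio = 0.80 x (Period 2 fraction) / f(N).

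Example at t = 4 days:
- 7 doses: f(7) = 1 - 2^(-1.75) = 0.703. With a = 1 the ratio is 0.80/0.703 = 1.14.
- With a = 0.5: 0.80 x (0.703 + 0.5 x 0.297)/0.703 = 0.97.
- With 10 doses and a = 1: f(10) = 0.823, and 0.80/0.823 = 0.97.

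Apparent change when the true change is -20%:

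| Assumed half-life | f(7) | 7 doses, full adherence (upper bound) | 7 doses, 50% adherence | 10 doses, full adherence |
|---|---|---|---|---|
| 1 day | 0.992 | -19% | -20% | -20% |
| 2 days | 0.912 | -12% | -16% | -17% |
| 4 days | 0.703 | +14% | -3% | -3% |
| 6 days | 0.555 | +44% | +12% | +17% |

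With no doses between periods (a = 0), both periods start from zero and the bias vanishes. At a half-life of 4 days, the same 20% fall thus reads anywhere from -20% (a = 0) to +14% (a = 1), depending only on unobserved dosing.

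**Half-life at which a fall is fully hidden** (a = 1): solve 2^(-N/t) = fall, so t = N x ln 2 / ln(1/fall).
- 7 doses: 2.8 days for an 18% fall, 3.0 for 20%, 4.3 for 32%.
- 10 doses: 4.0, 4.3 and 6.1 days.

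**Effect on power, as illustration only.** Read Table 8's difference of 20 as 20% of plateau, with SD 40, 42 pairs, 7 doses and full adherence. At 2 days the apparent fall is 91.2 - 80 = 11.2 and power is 42%, against 89% in the table. At 1 day the fall is 99.2 - 80 = 19.2 and power is 86%.

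**The case against.** The strongest reply is that a defect exists only if the PBMC half-life is long, and the documents do not say that it is. At 1 day nothing is wrong. This stands: what the text shows is an unjustified assumption, not a demonstrated error. A reader might infer that PBMC levels are known to be below plateau at one week; the documents do not support that.

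Nor should the +14% and +44% be taken as expected results. They require full adherence, exactly 7 doses and no earlier PrEP. Section 6.7 itself regards non-adherence as the likely main cause of low concentrations, and either 50% adherence or 10 doses turns +14% into about -3%. Lower adherence is only a partial defence, however: it shrinks the average bias but leaves Period 2 dependent on each participant's unobserved dosing.

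It is also tempting to read the qualifier in "plasma PrEP concentrations (and to an extent PBMC PrEP metabolite measurements) are more reflective of recent adherence" as an admission that one week is too short for PBMC. The sentence is about sensitivity to recent adherence, and it goes on to favour both matrices for use after short DOT. It neither concedes nor establishes steady state.

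Finally, much of a remedy is already in view. Plasma is a focus of the analysis and is what Table 8 powers; the objective is exploratory; and a PK model and the use of earlier studies' data are mentioned. That limits the consequence, but the PK model is conditional and no text commits to handling accumulation in the paired PBMC comparison.

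**Conclusion.** The point holds as a conditional risk of confounding in the PBMC comparison. The design facts are in the documents, and the direction is clear: incomplete accumulation in Period 1 raises the ratio and works against finding a fall. The size runs from negligible at a half-life of 1 day or less to, at the upper bound, a reversed sign at 4 days or more. It rests on an assumed half-life, first-order accumulation, the number of Period 1 doses, adherence between periods and no earlier PrEP. The same reasoning applies to FTC-TP and to the 1- and 4-hour PBMC values behind Cmax and AUC0-4.

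Two stronger conclusions go too far. One is that accumulation and hormone effect cannot be separated: the simple paired contrast does not separate them, but a model using dosing history could, given a stated half-life. The other is that the sub-study would answer its question wrongly: plasma TAF, TFV and FTC address it too and are not challenged here. This is a worthwhile low-cost improvement, not a threat to the trial's primary results.

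**What to change.** Change the analysis text in Sections 6.7 and 8.7.2, or the separate Statistical Analysis Plan to which Section 8.6 defers:

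1. Name the plasma trough as the pre/post contrast attributed to GAHT, with a sentence justifying one week of dosing for plasma, since no plasma half-life is given either.
2. Do not call PBMC values steady-state unless a stated and justified half-life supports it.
3. Analyse PBMC TFV-DP and FTC-TP with a non-steady-state model that uses the actual number of doses before each sample and the recorded dosing or PrEP use between periods and before entry, with a sensitivity range for the half-life. Self-report, the Enrollment and Week 13 dried blood spots, and the record of PrEP obtained outside the study are already collected. Otherwise, report the PBMC change as descriptive and not attributable to GAHT.
4. Reconcile Section 6.7, which has PBMC drawn pre-dose as well as at 1 and 4 hours, with Appendix Ic, which lists PBMC storage only at 1 and 4 hours. A PBMC trough needs the pre-dose sample.

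Items 1 to 3 change no visit, sample or dosing; item 4 aligns two existing descriptions. The cost is some wording and modest modelling work. The downside is that PBMC conclusions then depend on a stated accumulation assumption and on imperfect dosing records.
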